### **10.5.3 Other Secondary Efficacy Endpoints**

The primary analysis of other secondary endpoints will be performed using the full analysis set for non-psoriasis endpoints or the psoriasis efficacy analysis set for psoriasis endpoints. For binary endpoints, treatment effect will be tested using the stratified CMH test with BMI and prior non-biologic DMARD use as the stratification factors. For continuous endpoints that exhibit normal distribution, ANCOVA model will be used. The model will include treatment groups and baseline BMI and prior non-biologic DMARD as covariates. For continuous endpoints that are not normally distributed, endpoint data will be first transformed to their joint ranks and then further transformed by the Van der Waerden transformation to normalize them before applying ANCOVA model. The significance level for other secondary endpoints will be 0.05 without adjusting for multiplicity and p-values will therefore be treated as a descriptive statistic only.

Data will be analyzed as observed with no imputation for missing data.

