### **10.4 Planned Analyses**

#### **10.4.1 Primary Analysis**

The objective for the primary analysis is to evaluate the efficacy of etanercept plus methotrexate therapy and etanercept monotherapy compared to methotrexate monotherapy in subjects with PsA at week 24 as measured by the proportion of subjects achieving an ACR 20 response. The primary analysis will be performed when the last subject completes the week 48 visit or terminates early from the study, at which time the study will be unblinded.

For the primary and key secondary efficacy endpoints, treatment effect will be tested using a Bonferroni-based gatekeeping chain procedure ([Burman et al, 2009](#) and [Millen et al, 2011](#)) as described in Section 10.5.2 to control the family-wise 2-sided type one error rate at 0.05. Between-treatment comparisons will be made using the stratified Cochran-Mantel-Haenszel (CMH) test with baseline BMI and prior non-biologic DMARD use as the stratification factors. Missing data will be imputed using non-responder imputation for the primary analysis.

For other efficacy endpoints, the significance level will be 0.05 without adjusting for multiplicity and data will be analyzed as observed.

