### **10.5.2 Primary and Key Secondary Efficacy Endpoints**

The primary analysis for the primary endpoint and key secondary endpoints, ACR 20 response and MDA response at week 24, will be performed using the full analysis set. Treatment effect will be tested using the stratified CMH test with baseline BMI and prior non-biologic DMARD use as the stratification factors.

[figure not shown]
To control the family-wise 2-sided type one error rate at 0.05 for the multiple comparisons of the etanercept plus methotrexate therapy and etanercept monotherapy

groups with methotrexate monotherapy across the primary and key secondary endpoints, the hypotheses will be tested using a Bonferroni-based gatekeeping chain procedure (Burman et al, 2009 and Millen et al, 2011) as shown in Figure 1. This procedure will split alpha of 0.05 equally to test in parallel the primary and key secondary endpoints (ACR 20, MDA) for etanercept plus methotrexate therapy vs. methotrexate monotherapy and etanercept monotherapy vs. methotrexate monotherapy sequentially within each parallel path. If one of the parallel paths rejects both hypotheses sequentially, and the other parallel path has at least one hypothesis not rejected, then unspent alpha of 0.025 from the successful path will be propagated to the hypotheses in the other path to re-test them sequentially at a level of 0.05. For example, suppose the nominal p-values for hypotheses A1, B1, A2, and B2 (Figure 1) are 0.01, 0.02, 0.03, and 0.055, respectively. In the first round of testing, hypotheses A1 and B1 are rejected, whereas hypotheses A2 and B2 are not rejected. However, since both hypotheses A1 and B1 are rejected, the procedure gives a second chance to re-test hypotheses A2 and B2 (according to the left arm of the figure) at a lower threshold of 0.05 rather than the original threshold of 0.025. Note that in this example A2 is rejected and hypothesis B2 is not rejected.

Figure 1. Bonferroni-based Gatekeeping Chain Procedure

ETN: Etanercept; MTX: Methotrexate

For the primary analysis of the primary and key secondary endpoints, missing data will be imputed as nonresponder. Sensitivity analyses using observed data and using last observation carried forward imputation will also be performed.

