9.3.2 Missing Post-baseline Evaluation

Subjects with missing post-baseline efficacy data will be imputed as non-responder, ie, non-responder imputation (NRI) for the primary analysis of primary and key secondary efficacy endpoints (ACR 20 and MDA). Data will also be analyzed using multiple imputation (MI) as sensitivity analyses for primary and key secondary endpoints (ACR20 and MDA).

For analyses of other efficacy endpoints after week 24, data from subjects who remain in the double-blind period will be analyzed as observed with no imputation for missing data. Data from subjects who enter open-label rescue therapy will be imputed using last observation carried forward (LOCF).

For non-radiograph exploratory endpoints, data will be analyzed as observed without imputation for missing data.

For radiographic exploratory endpoints, data will be analyzed as observed with no imputation for missing data or for subjects who enter rescue treatment. In addition, data will be analyzed using LOCF imputation for missing radiographs and for subjects who enter rescue treatment as sensitivity analysis.

Baseline data will not be carried forward to any missing post-baseline value unless otherwise specified.

Missing post-baseline safety data will not be imputed.

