10.5.1 Analyses of Primary and Key Secondary Efficacy Endpoints

The primary analysis of the primary and key secondary endpoints, ACR 20 response and MDA response at week 24, will be performed using the full analysis set. Missing post-baseline data will be imputed using non-responder imputation (NRI) for the primary analysis. Treatment effect will be tested using the stratified Cochran-Mantel-Haenszel (CMH) test with baseline BMI and prior non-biologic DMARD use as the stratification factors.

[figure not shown]
To control the family-wise 2-sided type one error rate at 0.05 for the multiple comparisons of the etanercept plus methotrexate therapy and etanercept monotherapy groups with methotrexate monotherapy across the primary and key secondary endpoints, the hypotheses will be tested using a Bonferroni-based gatekeeping chain procedure ([Burman et al 2009](#) and [Millen et al 2011](#)) as shown in [Figure 1](#). This procedure will split alpha of 0.05 equally to test in parallel the primary and key secondary endpoints (ACR 20, MDA) for etanercept plus methotrexate therapy vs. methotrexate monotherapy and etanercept monotherapy vs. methotrexate monotherapy sequentially

within each parallel path. If one of the parallel paths rejects both hypotheses sequentially, and the other parallel path has at least one hypothesis not rejected, then the unspent alpha of 0.025 from the successful path will be propagated to the hypotheses in the other path to re-test them sequentially at a level of 0.05. For example, suppose the nominal p-values for hypotheses A1, B1, A2, and B2 (Figure 1) are 0.01, 0.02, 0.03, and 0.055, respectively. In the first round of testing, hypotheses A1 and B1 are rejected, whereas hypotheses A2 and B2 are not rejected. However, since both hypotheses A1 and B1 are rejected, the procedure gives a second chance to re-test hypotheses A2 and B2 (according to the left arm of the figure) at a lower threshold of 0.05 rather than the original threshold of 0.025. Note that in this example A2 is rejected and hypothesis B2 is not rejected.

Figure 1. Bonferroni-based Gatekeeping Chain Procedure

ETN: Etanercept; MTX: Methotrexate

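### Missing data count as non-response for week-24 ACR 20 and MDA but are left out of the other responder endpoints, so nested response rates at one visit have different denominators and some descriptive tests are open to completer bias

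*Protocol*

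**What the plan says.** **Week-24 ACR 20 and MDA.** Protocol 10.5.2: "For the primary analysis of the primary and key secondary endpoints, missing data will be imputed as nonresponder". SAP 10.5.1 agrees: "Missing post-baseline data will be imputed using non-responder imputation (NRI) for the primary analysis". SAP 9.3.2 limits this rule to the primary and key secondary endpoints and adds multiple imputation as a sensitivity analysis for those two only.

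**Everything else, in the protocol.** Section 10.4.1: "For other efficacy endpoints, the significance level will be 0.05 without adjusting for multiplicity and data will be analyzed as observed". Section 10.5.3 repeats it for other secondary endpoints: "Data will be analyzed as observed with no imputation for missing data".

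**Everything else, in the SAP.** Section 9.3.2 gives a rule for other efficacy endpoints only after week 24: "data from subjects who remain in the double-blind period will be analyzed as observed with no imputation for missing data", with LOCF for subjects who enter rescue. It then adds: "For non-radiograph exploratory endpoints, data will be analyzed as observed without imputation for missing data". VLDA is listed as exploratory in SAP 4.1.5, so this last sentence covers it. The SAP states no rule for other secondary endpoints at or before week 24.

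**What is tested.** SAP 10.5.2 applies the stratified CMH test at week 24 to VLDA and to achievement of LDI = 0, SPARCC = 0 and mNAPSI = 0, with unadjusted, descriptive p-values. ACR 50/70, and ACR 20 and MDA at other visits, are only summarized.

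**The concern.** ACR 50 and ACR 70 are the ACR 20 definition with higher cut-offs. VLDA is MDA with all seven criteria required instead of five. A reader will set these rates side by side, yet ACR 20 and MDA include every randomized subject and the stricter levels include only those with a result. The share of ACR 20 responders who also reach ACR 50 would be overstated for that reason alone.

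For the endpoints that get a between-arm test, leaving out subjects without data conditions on something that happens after randomization. If loss is related to toxicity or lack of effect and differs between arms, the comparison is no longer between the randomized groups. Unequal loss is conceivable: SAP 9.4 itself plans an analysis for possible bias from methotrexate intolerance, and only two of the three arms are randomized to methotrexate. No missing-data sensitivity analysis is planned for these tests.

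**Working it through.** **1. The plan's own figure.** Inputs (Protocol 10.2): ACR 20 of 60% vs 44%, two-sided alpha 0.025, power 90%, dropout 10%. The two-proportion chi-square formula gives 240 per arm without continuity correction and 253 with it. 253 / (1 − 0.10) = 281.1, rounded up to 282, against the stated 280 or so. The figure reproduces. It concerns the primary endpoint only and does not change here.

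**2. Which rule applies at week 24.**

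| Endpoint | Rule | Source |
|---|---|---|
| ACR 20, MDA | NRI | Protocol 10.5.2; SAP 9.3.2, 10.5.1 |
| ACR 50, ACR 70 | As observed | Protocol 10.4.1, 10.5.3; SAP silent at week 24 |
| VLDA | As observed | SAP 9.3.2, exploratory rule |
| LDI = 0, SPARCC = 0, mNAPSI = 0 | As observed, by default | Added in SAP 4.1.3 with no week-24 SAP rule; Protocol 10.5.3 |

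ACR 20 and MDA before week 24 are as observed under the protocol. At weeks 36 and 48 subjects who have left are omitted, but rescued subjects are kept by LOCF. For exploratory endpoints after rescue, SAP 9.3.2 supports both LOCF and as observed.

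**3. Effect on the level.** NRI rate = as-observed rate × (1 − missing share). At 10% missing the factor is 1 / 0.9 = 1.11. In counts, an arm of 280 with 28 missing has 252 observed; 111 responders give 111 / 252 = 44.0% as observed and 111 / 280 = 39.6% by NRI.

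**4. Effect on the difference.** The documents give no assumed rates for the affected endpoints, so the planning rates for ACR 20 and MDA (Protocol 10.2) are borrowed as as-observed rates for illustration. The 5%/15% splits are assumptions; the documents give only 10% overall.

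| As-observed rates (etanercept mono vs methotrexate) | Missing (etanercept / methotrexate) | NRI rates | As-observed difference | NRI difference |
|---|---|---|---|---|
| 60% vs 44% | 10% / 10% | 54.0% vs 39.6% | 16.0 | 14.4 |
| 60% vs 44% | 5% / 15% | 57.0% vs 37.4% | 16.0 | 19.6 |
| 60% vs 44% | 15% / 5% | 51.0% vs 41.8% | 16.0 | 9.2 |
| 30% vs 15% | 10% / 10% | 27.0% vs 13.5% | 15.0 | 13.5 |
| 30% vs 15% | 5% / 15% | 28.5% vs 12.75% | 15.0 | 15.75 |
| 30% vs 15% | 15% / 5% | 25.5% vs 14.25% | 15.0 | 11.25 |

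Simplest case: 40% response among those observed in both arms, with 15% vs 5% missing. As observed the difference is 0. By NRI it is 0.40 × 0.85 = 34% vs 0.40 × 0.95 = 38%, or 4 points. The shift can favour either arm and is smaller where response rates are lower, as they must be for VLDA relative to MDA.

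**5. Who is left out.** Only subjects with no derivable result at the visit. SAP Appendix A sets MDA and VLDA to failure when some components are missing, and to missing only when all are. So a record lacking one component is a failure, while a subject with no data leaves the denominator.

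**The case against.** **Stopping treatment is not the same as missing data.** A reader might infer that everyone who stops for toxicity or lack of effect is dropped. The documents do not support that. Protocol 8.1 lets subjects stop product and continue assessments, and 12.4 requires data collection from subjects off therapy. The SAP visit windows count assessments on days 141 to 210 as week 24 (127 to 210 for SPARCC, dactylitis, mNAPSI, sPGA and BSA), so an early-termination visit in that range is used. ACR responses are resolved from partial data where possible. This stands and limits the number affected.

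**Part of the comparison can be recovered.** Protocol 10.5.2 plans an observed-data sensitivity analysis for ACR 20 and MDA, which would put them on the same basis as ACR 50/70. The SAP does not repeat it, and SAP Section 11 does not withdraw it. Planned tables also give frequencies, so a crude NRI rate is responders over the analysis-set total. This stands for descriptive rates, but it gives no second analysis for the tested endpoints.

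**The results are descriptive, and NRI is itself an assumption.** Both are true. NRI is not an unbiased reference: the 4-point gap arises because every missing subject is taken to have failed. The case for NRI here is consistency with the rule the plan already chose.

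**An artificial dip at week 24.** A reader might expect the ACR 20 curve to fall at week 24 from the change of rule. That needs a flat observed curve and material missingness at neighbouring visits, and the documents establish neither.

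**Conclusion.** The point holds in a limited form. Two missing-data rules apply to responder endpoints at the same visit, and nested responses therefore have different denominators. At the planned 10% missing the stricter levels read 1.11 times their NRI value. That factor is arithmetic, given that the 10% dropout means 10% without a result.

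The CMH tests of VLDA and the three score-of-zero endpoints are open to completer bias; the documents do not show that they carry it. Size and direction depend on missingness by arm, which is not given, and the unequal splits above are assumptions. A reader might go further and doubt the trial's main conclusions. That does not follow: the gatekeeping chain covers only week-24 ACR 20 and MDA, both under NRI, and the affected p-values are declared descriptive.

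Two gaps in the SAP add to the point: no week-24 rule for other secondary responder endpoints, and two overlapping rules for exploratory endpoints after rescue. A cheap improvement is worth making, short of a threat to the primary result.

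**What to change.** In SAP 9.3.2 and 10.5.2:

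- Make NRI the main analysis for all binary responder endpoints (ACR 20/50/70, MDA, VLDA, LDI = 0, SPARCC = 0, mNAPSI = 0, sPGA 0 or 1), within their analysis sets and at all visits. Subjects lost by weeks 36 and 48 then also count as non-responders. Stopping NRI at week 24 would only move the change of rule to the later visits.
- Replace the overlapping sentences on LOCF after rescue and as-observed exploratory data with one rule for binary endpoints after rescue.
- Keep the as-observed analysis as supportive, and report the denominator and the number missing by arm for each endpoint and visit.
- Record the change in SAP Section 11.

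The cost is SAP wording and reuse of the primary-endpoint code. Sample size and the confirmatory tests do not change. The downside is slightly lower reported response rates and wider reliance on the NRI assumption already used for the primary endpoint.

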### **10.5.4 Safety Endpoints**

Safety endpoints will be summarized descriptively for all subjects by treatment group based on the safety analysis set. Subject incidence of all treatment-emergent adverse events will be tabulated by system organ class and preferred term. Tables of fatal adverse events, serious adverse events, adverse events leading to withdrawal from investigational product or other protocol-required therapies, and significant treatment-emergent adverse events will also be provided.

Laboratory parameters with grade 3 or above will be summarized by study visit and treatment group. Vital signs will be reported in baseline summaries. Shift tables of the worst on-study laboratory toxicity for analytes of interest based on Common Toxicity Criteria relative to baseline will be tabulated by treatment group (as described in the SAP).

## **11. REGULATORY OBLIGATIONS**

### **11.1 Informed Consent**

An initial sample informed consent form is provided for the investigator to prepare the informed consent document to be used at his or her site. Updates to the template are to be communicated formally in writing from the Amgen **Global Clinical Trial** Manager to the investigator. The written informed consent document is to be prepared in the language(s) of the potential patient population.

Before a subject's participation in the clinical study, the investigator is responsible for obtaining written informed consent from the subject after adequate explanation of the aims, methods, anticipated benefits, and potential hazards of the study and before any protocol-specific screening procedures or any investigational product(s) is/are administered.

The investigator is also responsible for asking the subject if the subject has a primary care physician and if the subject agrees to have his/her primary care physician informed of the subject's participation in the clinical study. If the subject agrees to such notification, the investigator is to inform the subject's primary care physician of the subject's participation in the clinical study. If the subject does not have a primary care physician and the investigator will be acting in that capacity, the investigator is to document such in the subject's medical record.

The acquisition of informed consent and the subject's agreement or refusal of his/her notification of the primary care physician is to be documented in the subject's medical records, and the informed consent form is to be signed and personally dated by the subject and by the person who conducted the informed consent discussion. The original signed informed consent form is to be retained in accordance with institutional policy, and a copy of the signed consent form is to be provided to the subject.

#### **11.2 Institutional Review Board/Independent Ethics Committee**

A copy of the protocol, proposed informed consent form, other written subject information, and any proposed advertising material must be submitted to the IRB/IEC for written approval. A copy of the written approval of the protocol and informed consent form must be received by Amgen before recruitment of subjects into the study and shipment of Amgen investigational product.

The investigator must submit and, where necessary, obtain approval from the IRB/IEC for all subsequent protocol amendments and changes to the informed consent document. The investigator is to notify the IRB/IEC of deviations from the protocol or serious adverse events occurring at the site and other adverse event reports received from Amgen, in accordance with local procedures.

The investigator is responsible for obtaining annual IRB/IEC approval/renewal throughout the duration of the study. Copies of the investigator's reports and the IRB/IEC continuance of approval must be sent to Amgen.

### **11.3 Subject Confidentiality**

The investigator must ensure that the subject's confidentiality is maintained for documents submitted to Amgen.

- Subjects are to be identified by a unique subject identification number.
- Where permitted, date of birth is to be documented and formatted in accordance with local laws and regulations.
- On the CRF demographics page, in addition to the unique subject identification number, include the age at time of enrollment.
- For serious adverse events reported to Amgen, subjects are to be identified by their unique subject identification number, initials (for faxed reports, in accordance with local laws and regulations), and date of birth (in accordance with local laws and regulations).
- Documents that are not submitted to Amgen (eg, signed informed consent forms) are to be kept in confidence by the investigator, except as described below.

In compliance with Federal regulations/ICH GCP Guidelines, it is required that the investigator and institution permit authorized representatives of the company, of the regulatory agency(s), and the IRB/IEC direct access to review the subject's original medical records for verification of study-related procedures and data. Direct access includes examining, analyzing, verifying, and reproducing any records and reports that are important to the evaluation of the study. The investigator is obligated to inform and obtain the consent of the subject to permit such individuals to have access to his/her study-related records, including personal information.

### **11.4 Investigator Signatory Obligations**

Each clinical study report is to be signed by the investigator or, in the case of multi-center studies, the coordinating investigator.

The coordinating investigator, identified by Amgen, will be any or all of the following:

- a recognized expert in the therapeutic area
- an Investigator who provided significant contributions to either the design or interpretation of the study
- an Investigator contributing a high number of eligible subjects

## **12. ADMINISTRATIVE AND LEGAL OBLIGATIONS**

### **12.1 Protocol Amendments and Study Termination**

If Amgen amends the protocol, agreement from the Investigator must be obtained. The IRB/IEC must be informed of all amendments and give approval. The investigator must send a copy of the approval letter from the IRB/IEC to Amgen.

Amgen reserves the right to terminate the study at any time. Both Amgen and the Investigator reserve the right to terminate the Investigator's participation in the study according to the study contract. The investigator is to notify the IRB/IEC in writing of the study's completion or early termination and send a copy of the notification to Amgen. Subjects may be eligible for continued treatment with Amgen investigational product(s) by an extension protocol or as provided for by the local country's regulatory mechanism. However, Amgen reserves the unilateral right, at its sole discretion, to determine whether to supply Amgen investigational product(s) and by what mechanism, after termination of the study and before the product(s) is/are available commercially.

